16.0 STATISTICAL CONSIDERATIONS

We will employ the Simon's two-stage design for the phase II clinical trials. (Simon R. Optimal two-stage designs for phase II clinical trials. *Control Clin Trials* 1989; 10: 1-10.) This trial design maximizes the chances of detecting a true difference in the HPV-specific T cell frequencies in pre- and post-vaccination samples while minimizing the number of patients treated if there is no difference. We plan to enroll and vaccinate up to 22 HPV+ OPC patients. In parallel we also plan to enroll and collect samples from up to 10 un-vaccinated HPVOPC patients in the observational group.

(a) Definition of primary outcome/endpoint:

We will determine the rate of vaccine-induced T cell responses at the time of surgical resection. For evaluation of immune responses in the peripheral blood, for each patient, a vaccine-induced T cell response will be considered:

1. Any post-vaccination E6- or E7-specific T cell response frequency (response to E6 or E7 peptide pool, minus nonspecific background, measured by ELISPOT or intracellular cytokine staining) equal or greater to two times the initial pre-vaccination baseline response. Where two baseline measurements are available, the mean value will be used.
2. When pre-vaccination E6/E7-specific T cell responses are not observed, any post-vaccination response at least two-fold greater than the average value of nonspecific background (for ELISPOT, approx. 10-15 spots/well) will be considered a positive response.

Toxicity will be scored using the NCI CTCAE 4.0 criteria, with any grade 3 or 4 toxicity considered as an adverse outcome.

(b) Definition of secondary outcomes/endpoints:

1. We will determine the rate of vaccine-induced T cell responses at various time-points after surgery (3W, 6W, 3M, 6M, 12M). Otherwise as per the primary outcome/endpoint

(c) Analytic plan for primary objective:

For each patient, the baseline mean frequency +/- SD of peptide-specific IFN- γ and/or TNF α expressing T cells in the peripheral blood will be determined by averaging the results of 3 replicate assays. At each subsequent blood draw, the mean frequency +/- SD of IFN- γ positive T cells will be determined in an identical fashion, and vaccine-induced T cell responses determined as described above. The response to each peptide will be evaluated separately. While the ADXS 11-001 vaccine contains the HPV E7 protein, cross-reactive responses to E6 and other HPV proteins can be observed following vaccination (personal communication, [name], Advaxis Pharmaceuticals) so we will monitor responses to E6, E7 and E2 peptides.

The trial is designed to conclude that ADXS 11-001 vaccination is likely highly immunogenic and worth further investigation if the overall rate of vaccine-induced T cell responses is 75% or more. ADXS 11-001 vaccination will be deemed not worthy of further investigation if the overall rate of vaccine-induced T cell responses is less than 50%.

For this trial, we propose a maximum sample size of 22 subjects, with 9 eligible subjects accrued in the first stage and 13 eligible subjects accrued in the second stage. One interim monitoring will be performed at the end of the first stage. The trial will be terminated early if it is evident that the T cell response rate is lower than the acceptable level. Since we do not yet know when the peak effect of vaccination will be, we will consider any responses at time of surgery or at 3 or 6 weeks after surgery to "count" as positive vaccine-induced T cell responses. If responses in five (5) or fewer patients are observed during the first stage, we will conclude that ADXS 11-001 vaccination does not merit continued investigation due to lack of immunologic efficacy. Otherwise accrual will continue until a total of 22 evaluable patients have been vaccinated and assessed for T cell response and toxicity.

If after completion of accrual more than fourteen (14/22) patients have vaccine-induced T cell responses, we will conclude that ADXS 11-001 vaccination is sufficiently active to justify recommendation for future studies.

(d) Analytic plan for secondary objectives:

The frequency of ELISPOT-positive T cells in the peripheral blood will be determined as described above for each patient at baseline and at different time points after surgery (3W, 6W, 3M, 6M, 12M). The average number of ELISPOT-positive T cells in the baseline and post-surgical samples will be compared, with $p < 0.05$ by two-sided paired student's T test considered a statistically significant difference.

(e) Sample size justification:

Using this design for the primary objective, the type-I error is 10%, and the power is 80.7%. If the T cell response rate is indeed only 50%, then the probability to stop the trial at the end of first stage is 75%, and the expected sample size of 13.

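### The final go rule is one responder too strict for the quoted error rates: 15 or more of 22 gives a type I error of 5.2% and power of 75.6%, whereas the stated 10% and 80.7% belong to 14 or more

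*Combined protocol and SAP*

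**What the plan says.** Section 16.0 commits to a Simon design: "We will employ the Simon's two-stage design for the phase II clinical trials". Section 16.0(c) then sets out its parts:

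- **Rates.** The vaccine is "worth further investigation if the overall rate of vaccine-induced T cell responses is 75% or more". It "will be deemed not worthy of further investigation if the overall rate of vaccine-induced T cell responses is less than 50" per cent.
- **Stages.** The plan is for "a maximum sample size of 22 subjects, with 9 eligible subjects accrued in the first stage and 13 eligible subjects accrued in the second stage".
- **Interim rule.** The trial stops for lack of immunologic efficacy under this condition: "If responses in five (5) or fewer patients are observed during the first stage".
- **Final rule.** The vaccine is recommended for future studies under this condition: "If after completion of accrual more than fourteen (14/22) patients have vaccine-induced T cell responses".

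Section 16.0(e) gives the operating characteristics of this design: "the type-I error is 10%, and the power is 80.7" per cent. It adds that, at a true response rate of 50%, "the probability to stop the trial at the end of first stage is 75%, and the expected sample size of 13". Section 6.0 mentions the 9 and 13 patients and refers to statistical criteria without giving a cut-off, so the final threshold appears only in 16.0(c).

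**The concern.** In Simon's notation the final boundary r is the largest number of responders that still counts as failure, and success starts at r + 1. The written rule puts r at 14, so success starts at 15. The error rates in 16.0(e) should follow from that boundary, and they look too generous for it.

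If the boundary and the error rates come from different designs, one of them is wrong. Either the trial has less power than it claims, or its go threshold is misprinted by one. In both cases the status of exactly 14 of 22 is open, and it could end up being decided after the result is known.

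**Working it through.** **Inputs, all from section 16.0.** p0 = 0.50 and p1 = 0.75; n1 = 9, n2 = 13, N = 22; stop if X1 ≤ 5. Final rule as written: total ≥ 15. Stated: type I error 10%, power 80.7%, probability of early stopping at p0 75%, expected sample size at p0 13.

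**Formula.** With c the smallest total that counts as success,

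P(go | p) = Σ over x = 6 to 9 of P(X1 = x) × P(X2 ≥ c − x), where X1 ~ Bin(9, p) and X2 ~ Bin(13, p).

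The type I error is P(go | 0.50) and the power is P(go | 0.75).

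**Step 1: the stage 1 figures, to confirm the inputs.**

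- P(stop at stage 1 | 0.50) = P(X1 ≤ 5) = 0.746, against the stated 75%.
- Expected N at p0 = 9 + (1 − 0.746) × 13 = 12.3. The stated 13 is consistent with rounding up.

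Neither figure depends on the final cut-off. The stage 1 rule and the stage sizes have been read correctly.

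**Step 2: reproduce the stated error rates. They come out with c = 14.**

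| x | P(X1 = x), p = 0.50 | P(X2 ≥ 14 − x) | product | P(X1 = x), p = 0.75 | P(X2 ≥ 14 − x) | product |
|---|---|---|---|---|---|---|
| 6 | 0.16406 | 0.29053 | 0.04766 | 0.23360 | 0.91979 | 0.21486 |
| 7 | 0.07031 | 0.50000 | 0.03516 | 0.30034 | 0.97571 | 0.29304 |
| 8 | 0.01758 | 0.70947 | 0.01247 | 0.22525 | 0.99435 | 0.22398 |
| 9 | 0.00195 | 0.86658 | 0.00169 | 0.07508 | 0.99901 | 0.07501 |
| Sum | | | **0.0970** | | | **0.8069** |

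Power of 80.69% matches the stated 80.7% to the decimal, and 9.70% rounds to the stated 10%.

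**Step 3: the rule as written, c = 15.**

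| x | P(X1 = x), p = 0.50 | P(X2 ≥ 15 − x) | product | P(X1 = x), p = 0.75 | P(X2 ≥ 15 − x) | product |
|---|---|---|---|---|---|---|
| 6 | 0.16406 | 0.13342 | 0.02189 | 0.23360 | 0.79396 | 0.18547 |
| 7 | 0.07031 | 0.29053 | 0.02043 | 0.30034 | 0.91979 | 0.27625 |
| 8 | 0.01758 | 0.50000 | 0.00879 | 0.22525 | 0.97571 | 0.21978 |
| 9 | 0.00195 | 0.70947 | 0.00139 | 0.07508 | 0.99435 | 0.07466 |
| Sum | | | **0.0525** | | | **0.7562** |

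**Step 4: the outcome in dispute.** The probability of passing stage 1 and ending at exactly 14 of 22 (63.6%) is the difference between the two rules:

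- at p1: 0.8069 − 0.7562 = 0.0507, or 5.1%;
- at p0: 0.0970 − 0.0525 = 0.0445, or 4.4% (0.0970 and 0.0525 are rounded; the unrounded difference is 0.04449).

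**Step 5: other explanations tried.**

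- Neighbouring cut-offs, same stages and interim rule: 13 or more gives 14.9% and 82.7%; 16 or more gives 2.3% and 65.5%.
- No interim look, single stage of 22: 15 or more gives 6.7% and 83.8%; 14 or more gives 14.3% and 92.5%.
- Success at 15 or more with a different stage 1 boundary: 6.4% and 82.4% if stopping at 4 or fewer; 3.1% and 57.1% if stopping at 6 or fewer.
- A search over two-stage designs with N up to 35, type I error at most 10% and power at least 80% gives stopping at 5 of 9 and failure at 13 of 22 as the design with the smallest expected N at p0 (12.3). This is Simon's optimal design for these rates, and its success region starts at 14.

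None of the alternatives gives the stated pair of figures. The design with success at 14 or more does.

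**The case against.** The strongest reply is that this is a slip of wording and the design itself is sound. The bracketed 14/22 can be taken to show that 14 was meant to count, and the power figure shows that the calculation used 14 as the first success count. On that reading the trial has the power it claims. The likely origin is indeed a slip, but that is an inference. The operative words exclude 14, the bracket does not say otherwise, and no other section settles it.

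A second reply is that the literal rule is conservative, since it lowers the type I error from 9.7% to 5.2%, and that only one outcome is affected. Both parts are true. The interim rule, the stage sizes and the treatment of patients do not change either. The cost is on the other side: the chance of missing a vaccine with a true 75% response rate rises from 19.3% to 24.4%, and power drops below 80%.

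A third reply is that the text does not expressly call 14 of 22 a negative result, because an observed 63.6% is not below 50%. That is fair as to the wording. The result would fail the only condition for recommending the vaccine, which in a two-stage design of this kind is a no-go.

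**Conclusion.** The concern holds. The final threshold in 16.0(c) and the operating characteristics in 16.0(e) belong to two different designs. Applied as written, the rule has a type I error of 5.2% and power of 75.6%, so stated power is too high by 5.1 percentage points (80.7 − 75.6) and the stated type I error is nearly double the actual one. The quoted figures fit success at 14 or more of 22.

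This rests on taking 50% and 75% as the true null and target rates, on exactly 9 and 22 evaluable patients at the two analyses, and on the literal reading of the final rule. The inconsistency must be fixed because it sits in the primary decision rule, although it changes the conclusion for only one result, 14 of 22.

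**What to change.** Choose one of two edits before any response data are analysed:

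1. **Reword the rule in 16.0(c)** so that fourteen or more of 22 responders (at least 14/22) leads to the recommendation. Keep the figures in 16.0(e), preferably stating the type I error as 9.7% beside the power of 80.7%. This matches the design that was evidently calculated.
2. **Keep the rule at 15 or more** and restate 16.0(e) as type I error 5.2% and power 75.6%, accepting power below 80%.

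Under either option, give the cut-off as an inequality (≥ 14/22 or ≥ 15/22) so that the boundary case is clear. The early stopping probability and the expected sample size are the same under both and can stay as they are.

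The cost is one sentence in section 16.0, with no extra patients and no change to the interim rule.

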1.3 Secondary Aim

The secondary objective will be to determine vaccine-induced HPV E6/E7-specific CD8+ CTL responses in the blood at various timepoints after surgery, with respect to baseline levels, in vaccinated patients.

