1.4 Secondary Endpoint

The secondary endpoint will be the change in HPV E6/E7-specific CD8+ cytotoxic lymphocyte (CTL) responses in the peripheral blood at various times after surgery (3W, 6W, 3M, 6M, 12M), with respect to baseline in vaccinated patients.

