8.6 Following entrance into the study, appropriate patients will be assigned to the vaccine arm by the local site PI. This group will be compared with an observational group of similar patients that will be treated with transoral surgery without vaccination during the same period of time. Since the design of this study is to compare patients' pre- and post-treatment assay results rather than results from vaccinated versus unvaccinated patients, assignment to treatment or observational group will not be randomized. Rather we will offer enrollment in the observational group to patients who do not wish to receive the vaccine but are willing to enroll in the observational portion of this trial.

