11.1 POSTOPERATIVE ADJUVANT THERAPY AND CLINICAL FOLLOW-UP

1. Adjuvant radiation therapy or chemoradiation will be given to appropriate patients based on preoperative and pathological risk factors as per standard-of-care. Participation in this trial will in no way alter the decision to provide post-surgical radiation or chemoradiation. While there is some leeway based on clinical judgment, standard criteria for adjuvant therapy include: positive surgical margin; lymphovascular invasion (LVI); perineural

invasion (PNI); extracapsular spread (ECS) of lymph node metastases or matted lymph nodes; low (level IV) cervical lymph nodes; >2 positive lymph nodes. These criteria are fairly standard across many institutions. If adjuvant therapy is indicated, therapy usually begins 4 to 6 weeks after surgical resection.

2. Patients will undergo routine post-treatment clinical follow-up, which usually involves monthly visits for the first year and q2-3 month visits in the second year following treatment. Imaging is obtained at the discretion of the treatment team, but is generally obtained no less than q 3 months for the first 2 years after treatment.
3. Assessment of disease status (no evidence of disease / NED; recurrent disease; second primary upper aerodigestive tumor; other second primary cancer) is performed by the attending surgeon at each follow-up appointment, and recorded in the electronic medical record (EMR).

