12.2 OBSERVATIONAL GROUP

1. The day of screening will be considered “day 0”. Initial blood draw (Draw 1) will be obtained at screening.
2. Standard-of-care pre-treatment tumor biopsy will be performed in a timely fashion for those patients without a prior biopsy, whose prior biopsy is inadequate for clinical planning, or for whom prior biopsy material adequate for immunophenotyping by immunohistochemistry (IHC) is not available.
3. Draw # 2: Observational patients will NOT undergo this blood draw.
4. Draw # 3: Observational patients will NOT undergo this blood draw.
5. Draw #4 will be performed preoperatively, on the day of surgery prior to induction of anesthesia, or up to 72 hours prior to surgery.
6. Draw #5 will be performed 3 weeks (+/- 1 week) after surgery.
7. Draw #6 will be performed 6 weeks (+/- 1 week) after surgery, before radiation.
8. Draw #7 will be performed 3 months (+/- 3 weeks) after surgery.
9. Draw #8 will be performed 6 months (+/- 3 weeks) after surgery.
10. Draw #9 will be performed 12 months (+/- 4 weeks) after surgery.

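### The 3, 6 and 12 month T-cell results are framed as vaccine-induced, but the planned own-baseline test cannot separate the vaccine from surgery and adjuvant treatment

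*Combined protocol and SAP*

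**What the plan says.** **Aim and endpoint.** Section 1.3 sets out to determine "vaccine-induced HPV E6/E7-specific CD8+ CTL responses in the blood at various timepoints after surgery, with respect to baseline levels, in vaccinated patients". Section 1.4 measures the change "at various times after surgery (3W, 6W, 3M, 6M, 12M), with respect to baseline in vaccinated patients". Section 16.0(b) restates this as a rate of vaccine-induced responses at the same five times.

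**Analysis.** Section 16.0(d) says: "The average number of ELISPOT-positive T cells in the baseline and post-surgical samples will be compared", with p below 0.05 by "two-sided paired student's T test considered a statistically significant difference". Section 16.0 contains no stratum, covariate, censoring rule or sensitivity analysis for adjuvant treatment.

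**Adjuvant treatment.** Section 5.1 admits patients whether or not they will need it. Section 11.1 bases it on preoperative and pathological risk and adds: "If adjuvant therapy is indicated, therapy usually begins 4 to 6 weeks after surgical resection". Sections 12.1 and 12.2 require Draw #6, at six weeks, to precede radiation. They set no such condition for Draws #7 to #9.

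**Observational group.** Section 8.6 says of the vaccinated patients: "This group will be compared with an observational group of similar patients that will be treated with transoral surgery without vaccination". A later sentence in the same section says the design rests on each patient's results before and after treatment, not on vaccinated against unvaccinated. Under Section 12.2, observational patients give Draw 1 and Draws 4 to 9 at the same post-surgical times as vaccinated patients, for example "Draw #7 will be performed 3 months (+/- 3 weeks) after surgery".

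**The concern.** A paired comparison removes stable differences between patients. It does not remove the effect of anything that happens to a patient between the two samples. For the late draws, that includes two vaccinations, removal of the tumour and, in some patients, radiation or chemoradiation. The word vaccine-induced credits the whole change to the first of these.

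Followed as written, the plan could report a late fall as waning of the vaccine response when it reflects adjuvant treatment, or a late rise as durable vaccine immunity when it reflects something else. What is at stake is how the persistence result is interpreted. A partial reference for the non-vaccine time course may be available from the observational group, but Section 16.0 does not say how its blood results will be used.

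**Working it through.** The plan gives no sample size, SD, effect size or power for the secondary analysis, so there is no figure of its own to reproduce. Its stated type I error and power belong to the two-stage design for the primary endpoint.

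**1. Timing** (Sections 11.1 and 12.1; 3, 6 and 12 months taken as 13, 26 and 52 weeks after surgery)
- Usual adjuvant start: weeks 4 to 6.
- Draw #6: 6 ± 1 = weeks 5 to 7, to be taken before radiation.
- Draw #7: 13 ± 3 = weeks 10 to 16.
- Draw #8: 26 ± 3 = weeks 23 to 29.
- Draw #9: 52 ± 4 = weeks 48 to 56.

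The earliest Draw #7 is 10 − 6 = 4 weeks after the latest usual start. So 3 of the 5 secondary time points normally follow the start of adjuvant treatment in every patient who receives it. Whether Draw #7 falls during or after the course depends on course length, which the documents do not give. With an assumed 6 to 7 weeks, the course ends between weeks 4 + 6 = 10 and 6 + 7 = 13, so either is possible.

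**2. What each contrast estimates** (simple additive model)

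Let V be the vaccine effect, S the effect of surgery and time, f the share given adjuvant treatment and A its average effect in them.
- Mean late change, vaccinated: V + S + f·A. The paired test asks whether this sum is zero, not whether V is.
- Mean late change, observational: S′ + f′·A′.
- Difference: V + (S − S′) + (f·A − f′·A′). This equals V only if the non-vaccine parts are alike in the two groups.

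**3. Size under assumed shifts**

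Take V = 0, n = 22, two-sided 5%. Let d be the non-vaccine mean shift in SDs of the change. The rejection probability comes from a noncentral t with 21 degrees of freedom and noncentrality d√22; for d = 0.5 this is 0.5 × 4.69 = 2.35.

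| Assumed shift d (SD) | Probability that p < 0.05 |
|---|---|
| 0 | 5% |
| 0.2 | 15% |
| 0.3 | 27% |
| 0.5 | 61% |
| 0.8 | 95% |

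The result is the same for shifts in either direction. If only patients given adjuvant treatment shift (simulation, 40,000 trials per cell):

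| Share treated | Each shifts 0.5 SD | Each shifts 1.0 SD |
|---|---|---|
| 30% | 10% | 23% |
| 50% | 20% | 52% |
| 70% | 34% | 81% |

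Every shift and share here is an assumption.

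**4. What the observational group can add** (Section 16.0: up to 22 vaccinated, up to 10 observational)
- Two-sample t test on change: noncentrality d√(22 × 10 / 32) = 2.62d, with 30 degrees of freedom. 80% power needs d = 1.10 SD, against 0.63 SD for the paired test with 22. With 22 against 5 it needs 1.44 SD. At d = 0.8, power is 53% against 95%.
- Exact (Clopper-Pearson) upper 95% limit for zero responders among n: 1 − 0.025^(1/n). This is 31% for 0 of 10, 52% for 0 of 5 and 71% for 0 of 3. For 3 of 10 the interval is 7% to 65%.

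**The case against.** The strongest reply is that the within-patient comparison is deliberate. Section 8.6 says so, Sections 1.3 and 1.4 define the aim and endpoint against baseline in vaccinated patients, and Section 16.0(d) tests exactly that. This stands as a reason to keep the paired test. It does not answer what the change may be attributed to once adjuvant treatment lies between the samples.

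A second reply is that the observational group is a poor control. Section 6.0 makes it optional and at most 10, and Section 8.6 fills it with patients who did not want the vaccine. The six-month postoperative antibiotic course in Section 10.6 is specified for vaccinated patients only. This also stands: the group can show a non-vaccine time course but cannot isolate the vaccine effect. A reader might infer that the data to separate the effects are already in hand; they are not.

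A reader might also infer that the observational blood has no purpose. Section 6.0 gives a general one, understanding the immunology of unvaccinated patients, and the assays in Section 12.5 are not limited to vaccinated patients. What is missing is an analysis of it in Section 16.0.

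Finally, reading the late time points first in patients who never receive adjuvant treatment looks attractive, but Section 11.1 ties that treatment to pathological risk. Such a subset is selected, and the population would change from one time point to the next.

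**Conclusion.** The point holds as one of attribution. At 3, 6 and 12 months the planned test cannot distinguish a vaccine effect from the effects of surgery and adjuvant treatment, yet the plan calls the result vaccine-induced. It affects three of five secondary time points, in an unstated share of patients. The timing rests on Section 11.1's usual start, and the rejection rates rest wholly on assumed shifts and shares.

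Two stronger readings are not supported. A reader might infer that a late change is to be expected without the vaccine. Section 2.2 says only that anti-HPV responses can be found in patients with HPV-mediated tumours. It says nothing about how they move after resection or radiation, so the mixture could create a late signal, hide one, or matter little. A reader might also infer that the trial's decision is compromised. Section 16.0(c) counts only responses at surgery and at 3 and 6 weeks, and Draw #6 is meant to precede radiation, so the go/no-go rule is not touched by the 3 to 12 month results.

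**What to change.** Amend Section 16.0(d) before the batched samples are analysed. Leave the paired comparison and the go/no-go rule as they are.

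1. Report the 3, 6 and 12 month results also by adjuvant treatment received before the draw: none, radiation, chemoradiation. Label this descriptive, because adjuvant use depends on pathological risk.
2. Apply the Section 16.0(a) responder rule and the same change-from-baseline summary to observational Draws 4 to 9, and show them beside the vaccinated group with 95% intervals, labelled non-randomised and supportive. Use Draw 1 alone as baseline in both groups for this contrast. Vaccinated patients may have a two-draw average, while observational patients have no Draw 2.
3. Describe late results as changes from baseline, not as vaccine-induced, unless the contrast in item 2 supports attribution.
4. Reconcile the two statements in Section 8.6 on whether the groups are compared.

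**Cost.** SAP text and a few tables, with no new visits or samples. The calendars in Section 7.0 have no row for adjuvant treatment, so its type and start date must be taken from the clinical record. Intervals will be wide, and the late results will read as less conclusive than a single p-value would suggest.
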